Study Identification Information

This is the first step in your Human Research Application. You will automatically be guided to the appropriate forms needed to complete your submissions.

1.0 * Study Name:

The impact of a home-based pulmonary telerehabilitation program on muscle function and quality of life following acute exacerbations of chronic obstructive pulmonary disease

2.0 * Brief Description (using layman's terms) - 500 words or less:

COPD impacts a significant proportion of the veteran population. Acute exacerbations, or flare-ups, of COPD are associated with impaired muscle function and worse quality of life. Pulmonary rehabilitation, a formal exercise program for patients with lung disease that includes both endurance and strength training exercises, has been shown to improve muscle function and quality of life after an acute exacerbation of COPD. However, lack of geographically accessible rehabilitation facilities and/or transportation issues are often barriers to pulmonary rehabilitation attendance in the veteran population. This study will assess the feasibility and impact of an intention to treat, eight-week, three sessions per week, home-based, pulmonary telerehabilitation program in veterans with COPD following hospitalization for an acute exacerbation of their lung disease. We will measure adherence and satisfaction with the program and muscle strength, physical activity, quality of life, and exercise tolerance pre and post-intervention in veterans randomized to the pulmonary telerehabilitation arm versus veterans randomized to the control arm who do not participate in pulmonary rehabilitation.

3.0*** Is this research study a Greater than Minimal Risk Clinical Trial?** Yes No**4.0***** Is this study a Greater than Minimal Risk Comparative Effectiveness research?** Yes No**5.0***** Principal Investigator:**[name]**5.1***** VA hours per week the PI is devoted to project:**

4

5.2*** Is the PI working with ionizing radiation?** Yes No**5.3***** Is the PI working with biological hazards?** Yes No**5.4***** Is the PI shipping biological hazards?** Yes No

A completed and signed Research Financial Conflict of Interest Statement is required for all investigators (including Principal Investigators, Co-Principal Investigators, and Co-Investigators) listed on the study application. [**Financial Conflict of Interest Form-Nov. 2013**](#)

5.5 Upload Financial Conflict of Interest Statement:[SPiRE [name] FCOI OGE Form 450 Fillable PDF-VA 3-19-14.pdf\(0.01\)](#)**7.0 Type of Submission:**

Description

This is a new study. This has not previously been submitted to the IRB.

This is a new paper conversion. This study has been previously approved by the IRB.

If this is a 'New Paper Conversion' please include the MIRB Number:

Please upload a letter certifying that you have made no modifications or amendments in converting this research study from paper to electronic:

ID: Pro00002952

View: 1.0 Study Identification Information

Study Identification Information (Continued)**1.0**

We have the adequate number of qualified staff to conduct this study. Each participant will be enrolled in home telehealth and home telehealth equipment that includes a blood pressure cuff and pulse oximeter to allow monitoring of vital signs during the pulmonary telerehabilitation intervention will be provided to each participant (both control group and intervention group). We will use [name] (co-investigator) Keiser leg press to measure lower extremity strength. Activity monitors, cycle ergometers, and resistance bands have been budgeted for and will be purchased through grant funding.

If no, please describe the resources that will be needed and explain how the resources will be obtained before the study is initiated:

2.0 *** VAPHS requires that either the PI or co-PI have a *physical presence* at VAPHS. Please describe the role the PI and/or co-PI have at VAPHS with respect to clinical responsibilities or in relation to other research activities.**

[name] (PI) has a 5/8th appointment (3/8th research, 2/8 clinical) at VAPHS. As part of her clinical responsibilities, she is a facilitator in the fellows' outpatient pulmonary clinic 1/2 day per week and has her own outpatient pulmonary clinic 1/2 day per week. She is also the director of the pulmonary function lab.

3.0 *** Will off-site ancillary service facilities (e.g., radiology services, central labs, non VA space, etc) be used for this study?**

Yes No

If yes, please provide the location and a brief description of the project activities to be conducted at the off-site ancillary facilities:

4.0 * Will a firm be contracted to obtain consent from subjects, collect private individually identifiable information from human subjects, or be involved in activities that would institutionally engage the firm in human subjects' research?

Yes No

If yes, please provide a description of the contracted service(s):

* Please specify the IRB that has oversight of the firm's activity(ies):

Name of Site / Institution	IRB Approval Document	FWA Number
There are no items to display		

This is a single-center, randomized, unblinded pilot study of an eight-week home-based pulmonary telerehabilitation program versus usual care in male and female veterans with COPD initiated immediately following hospitalization with an AECOPD. Outcome measures will include change in physical activity levels, maximal handgrip and quadriceps muscle strength, functional exercise performance, and health-related quality of life scores following the pulmonary telerehabilitation intervention versus usual care.

5.0 * Will any of the research being conducted as a part of this study be used to fulfill academic requirements (e.g., master's thesis, dissertation, or other academic program requirements

necessary to obtain a degree/certification, etc.)?

Yes No

ID: Pro00002952

View: 1.6 (CR) Study Locations

Study Locations

1.0 * Please add the local sites where this study will be conducted:

Location

[View](#) VAPHS University Drive Division

If Other, Please Specify:

ID: Pro00002952

View: 1.6.1 (CR) Multi-Site Study

1.6.1 Multi-Site Study

1.0 * Is this a multi-site study:

Yes No

ID: Pro00002952

View: 1.7 Section Chief and Service Line VP approvals

Please upload the approval of the Section Chief, if applicable and the Service Line VP.

1.0 * Institutional Approval Document:

[[name] Conduct of Research PJS.pdf\(0.02\)](#)

ID: Pro00002952

View: 2 Study Objectives & Design

Study Summary

1.0 Funding End Date:

3/31/2021

2.0

*** Abstract. Please provide a brief description of the study.**

Pulmonary telerehabilitation programs have been shown to have a high acceptance and adherence rate and lead to improvement in exercise capacity and quality of life in stable COPD. However, data regarding the feasibility and impact of pulmonary telerehabilitation following hospitalization for an AECOPD on physical activity levels, muscle function, exercise capacity, and health-related quality of life are lacking. Our primary hypothesis is that a home-based pulmonary telerehabilitation program initiated at hospital discharge following an AECOPD is feasible in the veteran population and will result in increased physical activity and greater improvement in muscle function, exercise capacity, and health-related quality of life compared to usual care. We will test this hypothesis with the following specific aims: (1) To determine the feasibility of an eight-week home-based pulmonary telerehabilitation program in veterans with moderate to severe COPD initiated in the immediate post-hospitalization period following an AECOPD. (2) To determine physical activity levels and the magnitude and variability in changes of measurements of muscle strength, functional exercise performance, and health-related quality of life following an eight-week home-based pulmonary telerehabilitation program versus usual care initiated in veterans with moderate to severe COPD immediately following hospitalization for an AECOPD. We will randomize (1:1 allocation) 30 male and female veterans hospitalized with an AECOPD to either an eight-week, three sessions per week, home-based pulmonary telerehabilitation program that includes lower extremity endurance exercises with a cycle ergometer and upper and lower extremity strength training with 1:1 supervision via video conferencing with an exercise physiologist as well as an optional once -monthly support group via teleconferencing versus usual care. Changes from baseline in physical activity levels, handgrip and quadriceps muscle strength, exercise endurance, and health-related quality of life will be assessed following the pulmonary telerehabilitation program versus usual care. Findings from this project will contribute to the growing field of pulmonary telerehabilitation and will provide critical preliminary data for the design and implementation of a larger, randomized control trial assessing the impact of pulmonary telerehabilitation on long-term clinical outcomes following AECOPD.

3.0

*** Describe the study objectives. Please include primary aim and hypothesis, if applicable any secondary aims and hypotheses.**

A pulmonary telerehabilitation program provides a home-based option for patients unable or unwilling to participate in a traditional, center-based program. Studies have demonstrated that home-based pulmonary telerehabilitation programs are feasible, positively impact exercise endurance and quality of life measures, and are widely-accepted by patients *when initiated during periods of lung disease stability*. However, little is known regarding the feasibility or impact on physical activity, muscle function, exercise performance, and quality of life measures of a home-based pulmonary telerehabilitation program initiated immediately following an AECOPD. Consequently, we propose a two-year pilot study to evaluate the feasibility and impact of a home-based pulmonary telerehabilitation program on physical activity levels, muscle strength,

exercise performance, and quality of life measures in veterans with COPD following hospitalization with an AECOPD. Our aims include:

SA 1: To determine the feasibility of an eight-week home-based pulmonary telerehabilitation program in veterans with moderate to severe COPD initiated in the immediate post-hospitalization period following an AECOPD. *Hypothesis: An eight-week home-based pulmonary telerehabilitation program will have a high acceptance and adherence rate among veterans with moderate to severe COPD following hospitalization for an AECOPD.* We will track adherence to a home-based pulmonary telerehabilitation program consisting of eight weeks, three sessions per week of 1:1 supervised lower extremity endurance exercise and upper and lower extremity strength training, as well as an optional once-monthly support group via teleconferencing, immediately following hospitalization for an AECOPD. Exercise sessions will be conducted by an exercise physiologist via video conferencing. The support group will be conducted by the exercise physiologist or another staff member via teleconferencing. A satisfaction survey will be administered at the completion of the intervention. We will also assess factors (i.e. psychiatric attributes, social support) associated with adherence to obtain preliminary insights to optimize recruitment for a larger, randomized controlled trial.

SA 2: To determine physical activity levels and the magnitude and variability in changes of measurements of muscle strength, functional exercise performance, and health-related quality of life following an eight-week home-based pulmonary telerehabilitation program versus usual care initiated in veterans with moderate to severe COPD immediately following hospitalization for an AECOPD.

Hypothesis: Participants randomized to an eight-week, three times per week pulmonary telerehabilitation program will demonstrate increased physical activity levels and greater improvement in maximal handgrip and quadriceps muscle strength, six minute walk, one-minute sit-to-stand testing, and health-related quality of life scores at completion of the intervention compared to participants randomized to usual care. We will compare changes from baseline in physical activity levels measured by pedometer, maximal handgrip and quadriceps muscle strength, six minute walk, one-minute sit-to-stand repetitions, and St. George's Respiratory Questionnaire and Short-Form 36-item questionnaire scores in veterans with moderate to severe COPD following an eight-week pulmonary telerehabilitation program versus usual care initiated after hospitalization for an AECOPD. The effect size and variance of these measurements will be used for the statistical planning (i.e. sample size and power calculations) of a larger, randomized controlled trial.

4.0 * Provide a summary of the background of the study, and explain how this research will contribute to existing knowledge. Describe previous studies that provides a basis to show that the proposed research can be carried out without undue risk to human subjects.

Chronic obstructive pulmonary disease (COPD) is the third leading cause of death in the United States and is highly prevalent in the aging veteran population. Health care costs in COPD are largely attributable to

acute exacerbations of COPD (AECOPD), defined as an increase in shortness of breath, cough, and/or sputum production that is beyond typical day-to-day variability and usually requires a change in medication. In addition to loss of lung function, decreased quality of life, and increased mortality, AECOPD are associated with reduced physical activity, muscle dysfunction, and poorer health-related quality of life. Muscle loss and dysfunction have, in turn, been associated with increased mortality in patients with COPD. Outpatient pulmonary rehabilitation initiated in the immediate post-exacerbation period has been shown to have a positive impact on muscle

function, exercise endurance, and health-related quality of life. As such, consensus guidelines recommend the participation in a pulmonary rehabilitation program within three to four weeks of an acute exacerbation of COPD. However, efforts to initiate outpatient pulmonary rehabilitation in the post-exacerbation period are often hindered by lack of physician referral, limited patient access to pulmonary rehabilitation facilities, or low patient motivation. A home-based pulmonary telerehabilitation program initiated at hospital discharge may circumvent these barriers. Pulmonary telerehabilitation programs have been shown to be safe, have a high acceptance and adherence rate, and lead to improvement in exercise capacity and quality of life in stable COPD. However, data regarding the feasibility and impact of pulmonary telerehabilitation following hospitalization for an AECOPD on physical activity levels, muscle function, exercise capacity, and health-related quality of life are lacking.

5.0 *** Describe the overall significance of the research in terms of the problem to be studied and potential findings, as well as its relevance to the care of veterans, the VAPHS, and the VHA:**
COPD is prevalent and associated with high health care utilization and costs in the veteran population. As of 2014, 52% of the veterans seeking care within the VA system were 65 years of age or older. As the veteran population continues to age, this percentage and the burden of chronic diseases such as COPD are anticipated to increase. Pulmonary rehabilitation is a key component to the management of patients with COPD but is not always a feasible option for the veterans that we care for. Only one-quarter of veterans live within 60-minutes transit time from a VA medical facility and even a lesser proportion live within one-hour distance from a VA facility offering specialized medical services such as pulmonary rehabilitation. This distance creates a tremendous burden for patients attending outpatient pulmonary rehabilitation programs, which typically require attendance two to three times per week. While some veterans may be eligible for pulmonary rehabilitation provided at a nearby non-VA facility, others living in rural areas typically do not have access to any rehabilitation program. We propose to test the feasibility of a home-based, pulmonary telerehabilitation program that will solve the issue of geographical inaccessibility and provide a service that may have meaningful impacts on exercise capacity and quality of life in our veterans with COPD.

6.0 Please upload any additional documents:

Name	Version
There are no items to display	

1.0**Type of Submission:**

New study

If this is a 'New Paper Conversion' please include the MIRB Number:

Please upload a letter certifying that you have made no modifications or amendments in converting this research study from paper to electronic:

2.0 * Requested Review Type:

Name	
	Exempt
	Expedited
	Full IRB Review
	Not Human Subject Research

3.0

Please check which of the following Service Lines/Departments/Entities will be impacted or used in the conduct of this study		Upload Letter of Support
	Clinical Support	
	Medical Specialty	[name] Service Line Support Letter(0.01)
	Investigational Drug Service	
	Imaging	
	Community Based Care	
	Patient Care Services	
	Behavioral Health	
	Primary Care	
	Surgical Specialty	
	Critical Care	
	Clinical Trials Center	
	Regulatory Coordinator Support Core	
	Clinical Coordinator Support Core	

	Ancillary Support Core	
	Data Support Core	
	Research Registry Registry Number:	
	Other	

If Other, please specify:

ID: Pro00002952

View: 3 Research Design

Methods & Procedures

1.0

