Health-related quality of life assessments: Health-related quality of life will be assessed with the St. George's Respiratory Questionnaire (SGRQ) and the Short-Form 36-Item Questionnaire (SF-36) prior to hospital discharge and following eight weeks of either the pulmonary telerehabilitation intervention or usual care. The SGRQ is a disease-specific questionnaire validated to measure health status in patients with COPD. Total SGRQ scores range from 0-100 with higher scores indicating greater symptoms burden. The minimal clinically important difference is a difference of four points in the total SGRQ score. The SF-36 consists of 36 questions spanning nine health domains and is a valid measure of health-related quality of life in COPD that is responsive to change following a pulmonary rehabilitation intervention.

Participant satisfaction survey: Participants will be administered a survey by the study coordinator after completion of the eight-week pulmonary telerehabilitation intervention that will require them to respond to statements related to their satisfaction with the home-based program using a five point Likert scale (strongly agree, agree, neutral, disagree, strongly disagree). Statements will address ease of use of the video conferencing modality, acceptability of exercise components, perceptions of impact on muscle strength and exercise endurance, and willingness to participate in additional pulmonary telerehabilitation. Questions regarding social support, psychiatric attributes, and other factors potentially associated with program adherence will also be asked in order to gain preliminary insights to optimize recruitment for a larger, randomized controlled trial of pulmonary telerehabilitation.

Please upload a table of procedures if applicable.

The study procedures table must be completed for:

- All Greater than Minimal Risk (GTM) studies; and
- All Minimal Risk studies that use Standard of Care or Usual Care/Interventions.

Name	Modified Date
Table of procedures	3/2/2021 12:56 PM

2.0

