The distributional characteristics of the outcome measures and change in outcome measures between study groups will be determined using appropriate descriptive statistics (e.g. mean, median, standard deviation, range) and graphical summarizations (e.g. histograms, boxplots, line plots). The purpose of this pilot study is to generate preliminary data on the expected effect size and variance of the outcome measures to facilitate planning (i.e. sample size calculations and power analyses) of a larger, randomized controlled trial. As such, we acknowledge that, given our small sample size (n=30, 15 participants per group), we likely will not have the power to detect a significant statistical or clinical difference in outcome measures between the intervention and usual care groups. However, we will perform exploratory analyses to compare changes in outcome measures between groups using a Student's t-test or nonparametric tests when appropriate.

ID: Pro00002952

View: 5 Sub-Studies

1.0 * Is there a sub-study or are there sub-studies associated with this study?

There is no sub-study associated with this study.

ID: Pro00002952

View: 6 Study Population Summary

Study Population Summary

1.0 * What is the maximum number of subjects you plan to enroll at VAPHS?

We plan to enroll 38 participants, accounting for 25% attrition, to result in 30 participants (15 intervention, 15 control) completing baseline and eight-week follow up testing.

2.0

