*** Do you plan on enrolling patients into different categories:**

Yes No

If yes, please explain:

We will randomize 30 eligible participants hospitalized with an acute exacerbation of COPD in a 1:1 allocation to either the eight-week home-based pulmonary telerehabilitation program intervention versus usual care prior to hospital discharge.

3.0 If this is a multi-site study, indicate the projected total subject accrual:

N/A

4.0*** Please provide a justification for the sample size:**

To meet our recruitment goal of 30 subjects over a one-year time interval, we will be required to enroll an average of 2-3 participants per month. A review of our COPD admission data shows that the medicine service at the VAPHS admits a mean of 28.4 (SD 8.7, range 15-43) patients per month with a primary diagnosis of COPD with acute exacerbation. Therefore, we anticipate no difficulty with recruitment for this study. We have not performed a sample size calculation given that this is a pilot study to generate preliminary data for the planning of a larger randomized controlled trial (including data to calculate estimated sample size).

ID: Pro00002952

View: 6.1 Study Population

Study Population**1.0 * Check all that apply to describe your study population:**

Study Population

 Non-Veterans Special Populations **Veterans** Vulnerable populations Other**2.0 * Indicate the inclusion criteria for enrollment:**

(1) Male and female veterans age 40-80; (2) Moderate or severe COPD with a forced expiratory volume in 1 second - forced vital capacity ratio (FEV1/FVC) < 0.70 and FEV1 < 80% predicted; (3) Hospitalization with a primary diagnosis of AECOPD, defined as an increase in shortness of breath, cough, and/or sputum production beyond the normal day-to-day variation necessitating a change in regular medication when other causes of increased shortness of breath, cough, and/or sputum production have been ruled out; (4) Capable of operating a tablet independently with adequate vision and hearing. The inclusion criteria should select for COPD patients with significant pulmonary disease that fall within an age range where age-related changes in muscle function are not the dominating factor.

3.0 * Indicate exclusion criteria for enrollment:

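### The effect observed in about 15 participants per arm is too imprecise to size the larger trial, yet SA 2 and the analysis plan assign it that use

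*Combined protocol and SAP*

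**What the plan says.** In the study objectives (View 2, item 3.0), SA 2 ends with the intended use of its results: "The effect size and variance of these measurements will be used for the statistical planning (i.e. sample size and power calculations" for a larger randomised controlled trial. The analysis plan (View 4.1) repeats it: "The purpose of this pilot study is to generate preliminary data on the expected effect size and variance of the outcome measures", so that the larger trial can be planned.

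The sample is small by design. The analysis plan describes it as "given our small sample size (n=30, 15 participants per group", and the abstract gives 1:1 allocation. View 6, item 1.0 adds the allowance for loss: "We plan to enroll 38 participants, accounting for 25% attrition, to result in 30 participants (15 intervention, 15 control" with baseline and eight-week testing. There is no power-based justification (View 6, item 4.0): "We have not performed a sample size calculation given that this is a pilot study".

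The analysis plan accepts that power to detect a between-group difference will probably be lacking. It specifies descriptive statistics, plots, and exploratory t-tests or nonparametric tests on changes. It does not provide for a confidence interval around the between-arm difference, and it has no rule for turning the estimate into a sample size.

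One important difference is given, in the paragraph on health-related quality of life (View 4): "The minimal clinically important difference is a difference of four points in the total SGRQ score". It is not linked to planning.

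**The concern.** Low power for a test and imprecision of a planning input have the same cause but different consequences. The plan acknowledges the first and then assigns the estimate to the second. Required sample size varies with the inverse square of the effect, so a moderate error in the observed effect becomes a large error in the planned size. If the observed effect exceeds the true one by chance, the larger trial is underpowered. If it falls short, the trial is needlessly large, and if it is zero or in the wrong direction no size can be derived.

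This matters because planning the larger trial is the purpose that the analysis plan itself states for the pilot, alongside the feasibility aim in SA 1.

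**Working it through.** **The plan's own figure.** The only derived number is the enrolment of 38. Multiplying, 30 × 1.25 = 37.5, which rounds up to 38, so it is reproduced. Dividing, 30 / 0.75 = 40, and 38 × 0.75 = 28.5 completers. The gap is small, and 15 per arm is used below.

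**Inputs.** From the documents: 15 per arm analysed, 1:1 allocation, changes compared between arms. Assumed, because the documents do not give them: a next trial with a two-sided 5% level and 80% power, and true standardised effects d of 0.2, 0.3, 0.5 and 0.8.

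**Precision of the observed effect.** SE(d) = √(2/15 + d²/60). At d = 0.5 this is √(0.1333 + 0.0042) = 0.371, so the half-width is 1.96 × 0.371 = 0.73 SD. For the raw difference in SD units, the t-based half-width is 2.048 × √(2/15) = 0.75 SD.

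The table gives exact (noncentral t) intervals, with the next trial's size per arm from n = 2(1.96 + 0.8416)²/d² = 15.70/d²:

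| Observed d | 95% CI | n per arm at estimate | n at upper limit | n at lower limit |
|---|---|---|---|---|
| 0.3 | -0.42 to 1.02 | 175 | 16 | undefined |
| 0.5 | -0.23 to 1.22 | 63 | 11 | undefined |
| 0.8 | 0.05 to 1.54 | 25 | 7 | about 6,800 |

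**How often the next trial would be mis-sized.** 400,000 pilots were simulated per true effect, with 15 per arm. Each sized the next trial from its own observed effect and SD, and no progression rule was applied.

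| True d | Required n per arm | Planned n below half | Planned n above twice, or none possible | Outside half to twice | True power below 50% |
|---|---|---|---|---|---|
| 0.2 | 393 | 41% | 44% | 85% | 41% |
| 0.3 | 175 | 37% | 40% | 77% | 37% |
| 0.5 | 63 | 29% | 34% | 64% | 28% |
| 0.8 | 25 | 20% | 26% | 46% | 20% |

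All percentages are of all pilots. The observed effect is zero or wrong-signed, so that no size exists, in 29%, 20%, 9% and 1% of pilots respectively.

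*Hand check at d = 0.5.* Since n is proportional to 1/d², planned size leaves the half-to-twice band when the observed effect is above 0.5 × √2 = 0.707 or below 0.5/√2 = 0.354. With SE 0.371 these points lie 0.56 SE above and 0.39 SE below the truth. The tail areas are about 0.29 and 0.35, together 0.64, which agrees with the simulation.

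**The variance is a better input.** With 28 degrees of freedom the 95% interval for the SD is 0.79 to 1.35 times the estimate. Suppose the target difference is fixed in advance, only the pilot SD is used, and the true effect equals the target. Planned size is then within half to twice the requirement in 98.6% of pilots, and true power is below 50% in 1.1%. Using the upper one-sided 80% limit of the SD, √(28/χ²₀.₂₀,₂₈) = 1.14, mean true power is about 86%, with under 0.3% of trials below 50%.

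**Illustration on SGRQ.** The documents give no SD. For assumed SDs of 10 to 18 points, the half-width of the pilot's 95% interval is 0.748 × SD = 7.5 to 13.5 points, against the stated difference of 4.

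**The case against.** The strongest reply is that the text is looser than the concern suggests. The effect size and variance are to be used for planning, and the data are called preliminary. Nothing says that the point estimate alone will be used, or that intervals, important differences or outside evidence are excluded. The larger trial will have its own protocol and its own sample-size justification, and the pilot also serves feasibility. All of this is fair and limits how serious the point is. It does not remove a stated use of the observed effect that carries no safeguard in the text available. The admission of low power does not cover it.

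A reader might also infer things that the documents do not support:

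- **That the larger trial will go ahead only if the pilot looks favourable, or that a useful programme would be dropped after a chance null result.** No progression criterion is stated. Assuming one changes the figures, so none is used above.
- **That mis-sizing is likely whatever the truth.** It is the more likely outcome at true effects of 0.2 to 0.5 SD, but slightly under even (46%) at 0.8 SD.
- **That the larger trial should be sized on 4 SGRQ points.** The abstract says that it will concern long-term clinical outcomes, which need not include SGRQ. The quality-of-life paragraph also does not say whether 4 points is a between-arm or a within-patient difference.
- **That the pilot variance is equally unusable.** It is not, provided its uncertainty is allowed for.

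**Conclusion.** The point holds for the observed effect size. As a planning input it has a 95% interval of about ±0.73 to 0.75 SD. Sizing on it misses the required number by more than a factor of two, or gives no number, in 46% to 85% of pilots over true effects from 0.8 down to 0.2 SD. Errors occur in both directions.

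These figures assume 15 analysed per arm, roughly normal change scores, a next trial planned at 80% power and a two-sided 5% level, and use of the point estimate. Precision could be worse for quadriceps strength, because that test is optional. The eight-week effects are also a step removed from the long-term outcomes named for the larger trial.

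The consequence falls on the later trial. The change is worth making, but it is no obstacle to running this pilot.

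**What to change.** Amend SA 2 and the analysis plan along these lines:

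> Between-arm differences in change will be reported with 95% confidence intervals. The observed effect will not be used as the planning effect for the larger trial. That trial will be sized on a clinically important difference for its own primary outcome, fixed before the pilot data are reviewed. The pilot will supply the standard deviation, with allowance for its uncertainty (for example the upper one-sided 80% confidence limit), and the attrition and adherence rates.

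The 4-point SGRQ difference is a candidate only if SGRQ is that primary outcome and 4 points is justified as a between-arm difference. The pilot SD helps only if the outcome is one of the measures taken here. Otherwise the pilot's contribution is attrition and adherence. The 80% limit is one convention among several.

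For this pilot the cost is wording and the reporting of intervals. For the larger trial, the upper-limit SD raises the planned size by about 30% over the point-estimate SD (1.139² = 1.297), and the team must choose and justify an important difference for its outcome. Sizing this way does not protect power if the true effect is smaller than the chosen difference, but the trial is then powered for a difference judged worth detecting.
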